12.2.2. Medication Adherence as a Dimension

The measurement of medication adherence (see Section 8.2) will allow analyses within the oral medication group, as well as within the total combined sample, to examine the relationship of the variables of interest with degree of medication adherence.

12.3. Demographics and Baseline Data

Demographics and baseline characteristics such as gender, age, race, weight, height, and body-mass index will be summarized using descriptive statistics. Medical history will be summarized using the number of observations and percentage of patients reporting each category. Concomitant medications as well as any protocol deviations will be recorded.

12.4. Efficacy Analysis

The primary hypothesis, that the hazard function (i.e. the risk of an event per unit of time) of the two medication groups differs between AL-LAI than the ARI-ORAL group, will be examined in a Cox regression analysis on the time to first relapse. We will include medication group membership, participation status in the NIMH exercise study, and length of stabilization period as predictors in the model.

For the secondary hypotheses involving the MCCB composite score, the GFS: (Role) we will use general linear mixed models (GLMMs). We will include participation status in the NIMH exercise study, medication group as a between-patient variable and time as a within-patient

variable in the model, and time*group as a within-between interaction term. Additionally, we will include length of stabilization period as person level time invariant covariate. The primary effect of interest is the difference in the pattern of change over time of the dependent variable between the medication groups, i.e. the time*group interaction term. GLMMs properly account for correlations induced by repeated measurements within patients and automatically handle missing data, producing unbiased estimates as long as observations are missing at random. The GLMM will use Satterthwaite's approximation to estimate degrees of freedom for the tests of the fixed and random effects, and model the variance-covariance matrix as a Toeplitz matrix. If this assumption does not lead to convergence we will instead use compound symmetry. The secondary analyses will compare the change in the MCCB Composite score and GFS: (Role) ratings between the two medication groups over the 12-month study period.

The data analyses for the exploratory measures will parallel those of the secondary measures.

All statistical tests and confidence intervals, unless stated otherwise, will be two-sided and will be set at $\alpha=0.05$.

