Randomization to ARI-ORAL: Patients will continue with ARI-ORAL doses within the recommended oral dosage range for the treatment of schizophrenia (10-30mg/day) with the usual starting dosage of 10 mg/day. ARI-ORAL dosage will be flexible and dosage will be at the discretion of the treating psychiatrist. Patients assigned to this treatment arm will receive a written prescription for a 30-day supply along with a medication coupon so there will be no medication cost to the patient.

Discontinuation of Assigned Treatment

Both groups will remain on their assigned treatment for 12 months or discontinue their assigned medication early. The reason(s) for early discontinuation of initial antipsychotic will be recorded, including whether it is initiated by the clinician or patient, and whether it is efficacy or tolerability related. Patients will be assessed for the reason for discontinuation using a version of the All-Cause Discontinuation (ACD) measure that was the primary outcome of the CATIE schizophrenia study. If a switch to another antipsychotic medication is warranted, the new therapy will be determined by the prescribing psychiatrist's judgment using the medication selection recommendation adapted from NAVIGATE pharmacologic treatment manual developed as part of the Recovery After an Initial Schizophrenia Episode (RAISE) study intervention groups. Patients discontinuing study drug after Randomization, but remaining in active treatment and follow-up, may be prescribed any first-line oral antipsychotic within the prescribing information dosage for schizophrenia. Patients will be encouraged to stay in the study for the remainder of the 12-month Treatment period and will be administered all of the scheduled assessments even if the initial randomly assigned antipsychotic medication is discontinued by the treating psychiatrist.

Symptom assessments will occur every two weeks, functional endpoint will occur every three months, and the cognitive endpoint will occur at baseline and at the 6- and 12-month points. All patients participating in the protocol will be invited to concurrently participate in a separate NIMH-funded psychosocial intervention protocol comparing the effectiveness of computerized cognitive training with and without aerobic exercise training.

Number of Patients Planned: Approximately 128 patients enrolled into the Stabilization period for final randomized sample of 90 (45 in each group) with a target of 14 relapses

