7. STUDY DESIGN

7.1. Overall Study Design

[figure not shown]
This is an open-label study of approximately 90 patients with schizophrenia who will be randomly assigned to 12 months of treatment with either ARI-ORAL or AL-LAI to take place at the UCLA Aftercare Research Program ([name]), which is a program that specializes in the treatment and study of individuals with a recent onset of schizophrenia. The study design is presented in [Figure 1](#). Potential patients will be evaluated for eligibility according to the inclusion and exclusion criteria at Screening.

For patients who have never taken aripiprazole, tolerability must be established during the Stabilization period. The Stabilization period will be once-a-day ARI-ORAL with flexible dosing. All patients will receive ARI-ORAL for at least two weeks to establish full tolerability before Randomization, and patients who cannot tolerate ARI-ORAL 10 mg/day will not be randomized. Eligibility to be randomized will be determined at the end of the Stabilization period of up to 90 days.

The Stabilization period will allow time for the oral antipsychotic medication to be cross-tapered to ARI-ORAL, if needed, and allow time for the patient to obtain some clinical stability prior to Randomization. Further, the Stabilization period will allow the baseline testing for this and the overlapping National Institute of Medical Health (NIMH) protocol to occur at a pace appropriate for someone who is in the middle, or tail-end of, a psychotic episode.

Randomization (1:1 [AL-LAI: ARI-ORAL]) will take place after the Stabilization period. The NIMH overlapping study is a psychosocial intervention treatment. To balance the overlapping NIMH treatment groups in the AL-LAI and ARI-ORAL treatment groups, the randomization of patients in the APPRIASE study will be stratified by their participating role in the NIMH study (randomized to computerized cognitive training with or without aerobic exercise). Once randomized, patients will be treated per prescribing recommendations for a 12-month Treatment period.

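### In the MCCB and GFS: Role mixed models the NIMH factor is a time-constant main effect only, so it adds essentially nothing to the time × group test; the cost is some precision, not bias

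*Combined protocol and SAP*

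**What the plan says.** The Synopsis and Section 12.4 list the same terms for the MCCB and GFS: Role models. Section 12.4 reads "We will include participation status in the NIMH exercise study, medication group as a between-patient variable and time as a within-patient" variable, and then "time*group as a within-between interaction term". Length of stabilization is added as a time-invariant covariate. Group here means medication group, because "The primary effect of interest is the difference in the pattern of change over time of the dependent variable between the medication groups". No NIMH × time term appears in either place. For the covariance, the plan will "model the variance-covariance matrix as a Toeplitz matrix", with compound symmetry as the fallback.

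On the design side, Section 7.1 says that randomisation "will be stratified by their participating role in the NIMH study", explained there as training with or without aerobic exercise, and gives balance of the NIMH arms across the medication arms as the purpose. The Synopsis describes the NIMH protocol as concurrent, offered by invitation, and "comparing the effectiveness of computerized cognitive training with and without aerobic exercise training".

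Two related points are unsettled. Participation status is never defined: it could be yes/no or the NIMH arm. And the Synopsis design description and Section 7.4.13 put the randomisations in the other order, with each medication group then randomised to an NIMH condition. Section 7.4.13 also names the conditions differently (cognitive remediation or healthy behavior training).

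**The concern.** The secondary hypotheses are about change. A main effect for NIMH status moves a patient's level by the same amount at every visit, so it cannot explain why one patient changes more than another. The NIMH study delivers cognitive training with or without exercise during the same period, and the MCCB measures cognition. If the NIMH arm affects MCCB change, the planned covariate does not remove that source of variation from the test it was presumably included to help.

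At stake is precision on the two secondary endpoints, chiefly the MCCB. Stratifying the randomisation by a factor and then leaving it out of the tested contrast gives up the precision that the stratification makes available, and leaves a test that rejects less often than its nominal level when there is no drug effect.

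**Working it through.** **Inputs from the documents.** MCCB: r = 0.89, two-sided alpha 0.025, anticipated d = 0.50 (f = 0.25), three time points (baseline, months 6 and 12). GFS: Role: r = 0.5, alpha 0.025, anticipated d = 0.63, five time points. Sample size 45 per arm with 36 completers (Synopsis); the Table 7 title says 35 and 28.

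**Assumption.** The effect e of the NIMH arm on change, in raw SD units, is not in the documents. I use 0.2, 0.3 and 0.5, with a 50:50 NIMH split.

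**Step 1: the plan's own figure.** For the interaction F test, λ = f²·N·m/(1−r), with m−1 and (N−2)(m−1) degrees of freedom. For the MCCB at f = 0.09, m = 3 and N = 56, λ = 0.0081 × 56 × 3 / 0.11 = 12.4 and power is 0.818. This reproduces the plan's power of at least 0.80, at the Table 7 sample size. At N = 72 power is 0.915. Power above 0.99 at f = 0.25 also reproduces.

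**Step 2: the main effect cancels.** Write the mean for patient i at visit t as μ(t) + γX(i) + δ(t)G(i), where X is NIMH status and G is medication group. The test concerns δ(12) − δ(0). Differencing visits removes γX(i), so with complete data the term drops out. Simulated Toeplitz REML fits (72 patients, three visits, r = 0.89, 40 runs per scenario) agree. With complete data, the estimates with and without the NIMH main effect differ by about 1e-15 and the SE ratio is 1.000. With 20% dropout, the largest difference is 0.008 SD and the mean SE ratio is 0.9995 to 0.9999. Adding NIMH × time with e = 0.5 takes the SE to 0.874 (complete data) or 0.888 (20% dropout) of its value without any NIMH term.

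**Step 3: variance left in the error term.** The variance of change is 2(1−r): 0.22 for the MCCB and 1.00 for GFS: Role. A 50:50 factor with effect e adds e²/4. The SE ratio is √[2(1−r) / (2(1−r) + e²/4)].

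| Assumed e | Added variance | MCCB share of change variance | MCCB SE reduction | GFS: Role SE reduction |
|---|---|---|---|---|
| 0.2 | 0.0100 | 4% | 2% | 0.5% |
| 0.3 | 0.0225 | 9% | 5% | 1% |
| 0.5 | 0.0625 | 22% | 12% | 3% |

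**Step 4: power.** Noncentral t on baseline-to-month-12 change, 36 per arm, 70 df, alpha 0.025, SE = √(2v/36). With the interaction, the MCCB SE is √(0.44/36) = 0.111. Without it, at e = 0.5, it is √(0.565/36) = 0.125.

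| Drug effect | Without, e = 0.2 / 0.3 / 0.5 | With NIMH × time |
|---|---|---|
| MCCB 0.50 (plan) | 0.982 / 0.977 / 0.953 | 0.986 |
| MCCB 0.30 (not the plan's) | 0.642 / 0.617 / 0.544 | 0.664 |
| GFS: Role 0.63 (plan) | 0.644 / 0.638 / 0.620 | 0.649 |

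At 28 per arm, MCCB d = 0.50 and e = 0.3, power goes from 0.929 to 0.951. Read these rows for the before-and-after difference only. A single change contrast that takes d as raw SD units is not the plan's f-based calculation, so 0.649 does not contradict its figure above 99%.

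**Step 5: balanced or chance allocation.** With balanced strata the MCCB estimate varies with SE 0.111 whatever e is, while the planned model reports 0.113, 0.116 or 0.125. The true size of the 0.025 test is then about 0.022, 0.019 or 0.011. Multiplying the critical value of about 2.29 by 1.022, 1.050 or 1.133 gives power without the term of 0.984, 0.981 or 0.971 at d = 0.50, slightly better than in the table. If allocation did not balance the NIMH arms, chance imbalance at e = 0.5 would add noise with SD 0.5 × √(2 × 0.25/36) = 0.059. Then √(0.111² + 0.059²) = 0.125, which is the SE that the planned model reports. Neither case produces bias.

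**The case against.** The strongest reply is that this is an optional precision gain on secondary endpoints. Much of that stands.

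- **Bias.** A reader might infer that NIMH imbalance contaminates the medication comparison. The documents do not support that: Section 7.1 stratifies precisely to prevent it. Only residual imbalance remains, from dropout, incomplete strata or the reversed order in the Synopsis and Section 7.4.13, and it adds noise rather than systematic error. The reversed order would not itself create imbalance if NIMH allocation were blocked within medication group, which the documents do not say.
- **Merged arms.** A reader might also infer that the covariate lumps the two NIMH arms together. The term is undefined and may be shorthand for the NIMH role of Section 7.1. What can be said is that its levels need defining.
- **Size.** Both NIMH arms receive training as Section 7.1 describes them, so e reflects only the added exercise. An e of 0.5 SD would equal the drug effect that the trial anticipates for the MCCB. At the planned drug effect, power exceeds 0.95 with or without the term at 36 per arm. The 12-point gain at 0.3 SD needs both a smaller drug effect than planned and the largest e considered.
- **GFS: Role and Cox.** The GFS: Role gain is slight. In the Cox model a main effect is the ordinary form, so nothing is wrong there beyond the undefined coding.

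The reply does not answer the algebra: as specified, the NIMH term does essentially no work in the test of interest.

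**Conclusion.** The concern holds as a matter of precision. The NIMH factor by which randomisation is stratified does not reach the time × group test: exactly so with complete data, and to within 0.01 SD with 20% dropout. If the NIMH arm affects change, the planned analysis has a somewhat wide standard error and, with balanced strata, a conservative test. For the MCCB, at the plan's d = 0.50 and 36 per arm, the cost is 0.4 to 3.3 power points for e of 0.2 to 0.5 SD; it is larger for smaller drug effects. For GFS: Role it is 0.5 to 2.9 points at d = 0.63. With e = 0 it is nil.

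These sizes rest on an assumed e, a 50:50 NIMH split and a change-score approximation. The stronger conclusions, that the estimates are biased, that secondary power is seriously short for this reason, or that the primary Cox test is invalid, do not follow from the documents. The point is still worth acting on, because the correction is specific and nearly free.

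**What to change.** In the Synopsis and Section 12.4, replace NIMH participation status in both mixed models by the NIMH stratum used at randomisation, with its levels listed (training, training plus exercise, and a non-participant level if there is one), and add stratum × time. State beforehand how sparse strata would be merged. Use the same coding in the Cox model, as a main effect only, for consistency. Reconcile Section 7.1 with the Synopsis design description and Section 7.4.13 on the order of the randomisations and the names of the NIMH conditions, so that the stratum is unambiguous.

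The cost is (levels − 1) × (visits − 1) fixed-effect degrees of freedom: 2 or 4 for the MCCB with three visits, and 4 or 8 for GFS: Role with five. No new data are needed, and the wording change is short. It should be made before the analysis begins.

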The secondary hypotheses of the MCCB composite score and the GFS (Role) rating will be examined in general linear mixed models (GLMMs). We will include participation status in the NIMH exercise study, medication group as a between-patient variable and time as a within-patient variable in the model, and time*group as a within-between interaction term. Additionally, we will include length of stabilization period as a person level time invariant covariate. The primary effect of interest is the difference in the pattern of change over time of the dependent variable between the medication groups (i.e. the time*group interaction term). GLMMs properly account for correlations induced by repeated measurements within patients and automatically handle missing data, producing unbiased estimates as long as observations are missing at random. The GLMM will use Satterthwaite's approximation to estimate degrees of freedom for the tests of the fixed and random effects, and model the variance-covariance matrix as a Toeplitz matrix. If this assumption does not lead to convergence we will instead use compound symmetry. The secondary analyses will compare the change in the MCCB Composite score and GFS (Role) ratings between the two medication groups over the 12-month study period.

The data analytic methods for the exploratory measures will in general parallel those of the secondary measures.

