12. STATISTICS

12.1.1. Sample Size Considerations

Ninety first-episode patients will be randomized (1:1) fashion to either AL-LAI or ARI-ORAL, and based on our previous RCT, assume a 20% attrition rate over 12 months. Statistical power considerations are based on the effect sizes observed when comparing long-acting injectable risperidone vs. oral risperidone (survival analysis for psychotic relapse: 5% relapse in the risperidone long-acting injectable group and 33% relapse in the oral risperidone group). On the basis of hazard function rates of 5.0% (AL-LAI) and 33% (ARI-ORAL), the study has 87% power ($\alpha=0.05$). On a more conservative basis of hazard function rates of 7.5% (AL-LAI) and 33% (ARI-ORAL), the study has 78% power ($\alpha=0.05$) (Table 6).

For the secondary hypothesis for the relative changes in the MCCB Composite score and the GFS: Role, we will use a two-sided significance level of $\alpha=.025$ to account for type 1 error inflation. For the MCCB Composite score, assuming a within-patient correlation between repeated measurements of $r=0.89$ (based on a prior study), the proposed design provides us sufficient power ($>=0.80$) for Group X Time interaction effects as small as Cohen's $f=0.09$. Based on our previous work, we anticipate a medium effect size (Cohen's $f=0.25$ or $d=0.50$), and this design provides a power of >0.99 for an effect of this size. For the GFS rating, if we assume a within-patient correlation of $r=0.5$, with $\alpha=0.025$, our GLMM will have 80% power to detect an interaction corresponding to an effect size of $f=.20$. Based on a prior study, we anticipate an effect size of $f=0.32$ or $d=0.63$ for the GFS: Role ratings, for which we would have $>99\%$ power.

Thus, for both primary and secondary outcome measures we will be able to detect differential treatment effects based on our proposed design and expected sample size.

Table 7: Power Calculations by Analysis with N=35 Each Group (N=28 at completion)

Clinical assumption for each group			Power	Alpha
Primary Analyses	Hazard ratio between the two groups	Difference in hazard functions similar to that of our previous RCT: Long-acting injectable: 5%, oral antipsychotic: 33%	87%	.05
		For rates of hazard function rates of 7.5% (AL-LAI) and 33% (ARI-ORAL)	78%	
Secondary Analyses: MCCB Overall Composite score	change from BL in MCCB Overall Composite score	Based on our previous work, we anticipate a medium effect size (Cohen's $f=.25$ or $d=.50$)	>99%	.025

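### The compound-symmetry fallback for the secondary mixed models can exceed the stated 2.5% error level if within-patient correlation falls with time, and the plan gives it no robust protection

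*Combined protocol and SAP*

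**What the plan says.** Section 12.4 tests MCCB and GFS: Role in general linear mixed models. The effect of interest is the time-by-group interaction, with Satterthwaite degrees of freedom. The first-choice structure is to "model the variance-covariance matrix as a Toeplitz matrix" (Synopsis, repeated in Section 12.4). The only alternative is: "If this assumption does not lead to convergence we will instead use compound symmetry". No sandwich errors, unstructured or unequal-variance option, or intermediate structure is given, and the text does not say whether time is categorical or linear. Exploratory measures follow the same approach.

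On the error level, Section 12.1.1 says "we will use a two-sided significance level of $\alpha=.025$ to account for type 1 error inflation". It gives one correlation per endpoint. For MCCB it is "assuming a within-patient correlation between repeated measurements of $r=0.89$ (based on a prior study"), and for GFS: Role the power statement begins "if we assume a within-patient correlation of $r=0.5$, with $\alpha=0.025$, our GLMM will have 80% power to detect". No lag-specific correlations or visit-specific SDs appear.

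Table 2 schedules MCCB at baseline and Months 6 and 12 (3 visits), and GFS: Role at baseline and Months 3, 6, 9 and 12 (5 visits).

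**The concern.** Ratings taken close together are often more alike than ratings a year apart. Compound symmetry cannot represent this. It replaces every correlation by one average, so it understates the variance of a change over a long interval. The 0.025 level exists to control false positives over two secondary endpoints, and a fallback that does not hold that level works against it. A false claim of a functional or cognitive advantage for AL-LAI is what is at stake.

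A lesser question concerns the first choice. Ordinary Toeplitz imposes the same variance at every visit. Section 7.1 describes baseline testing as proceeding "at a pace appropriate for someone who is in the middle, or tail-end of, a psychotic episode", so baseline spread could differ from later spread, although the documents give no SDs with which to judge this.

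**Working it through.** **Inputs.** Two-sided level 0.025, so z = 2.2414. Average correlation 0.5 (GFS: Role) and 0.89 (MCCB), from Section 12.1.1. Visits: 5 and 3. N = 90 randomised, or 36 completers per arm.

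**Formula.** Let R be the true correlation matrix, r̄ its average off-diagonal value and c a contrast over visits that sums to zero. With complete data and equal variances, the true variance is proportional to c′Rc. Compound symmetry reports (1 − r̄)c′c. With ratio k = c′Rc / [(1 − r̄)c′c], the large-sample error is 2[1 − Φ(2.2414/√k)].

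- Month 12 minus baseline: k = (1 − ρ_last)/(1 − r̄), where ρ_last is the correlation at the longest lag.
- GFS: Role slope, c = (−2, −1, 0, 1, 2): c′Rc = 10 + 2(4ρ₁ − ρ₂ − 4ρ₃ − 4ρ₄), against 10(1 − r̄).

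**Constant correlation, as the plan assumes.** With r = 0.5 throughout, k = 1 and the error is 2.5%. Simulation (200,000 runs, N = 90) agrees: 2.51% (4-df test), 2.55% (slope), 2.48% (Month 12 minus baseline).

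**One decaying pattern in full.** Lag correlations .60, .50, .40, .30 still average 0.5: (4×.60 + 3×.50 + 2×.40 + .30)/10 = 0.5.

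- Month 12: k = 0.70/0.50 = 1.40; 2.2414/√1.40 = 1.894; error 5.8%.
- Slope: c′Rc = 10 + 2(2.4 − 0.5 − 1.6 − 1.2) = 8.2; k = 8.2/5 = 1.64; 2.2414/√1.64 = 1.750; error 8.0%.

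**GFS: Role under compound symmetry, average correlation 0.5** (simulation, N = 90; k by the formula above):

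| Lag correlations (assumed) | 4-df test | Month 12 − baseline (k) | Slope (k) |
|---|---|---|---|
| .50 constant | 2.5% | 2.5% (1.00) | 2.5% (1.00) |
| .55 .50 .45 .40 | 2.7% | 4.0% (1.20) | 5.1% (1.32) |
| .60 .50 .40 .30 | 3.2% | 5.8% (1.40) | 8.0% (1.64) |
| .65 .50 .35 .20 | 3.9% | 7.6% (1.60) | 10.9% (1.96) |
| AR(1), ρ = .684 | 4.2% | 7.3% (1.56) | 11.8% (2.04) |

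If the average is allowed to move from 0.5, AR(1) with ρ from 0.6 to 0.9 (36 per arm) gives 3.8-5.5%, 6.2-10.3% and 10-15% for the three columns. With 20% random dropout and ρ = .684, the 4-df test is 4.4% and the slope 12.0%.

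**MCCB under compound symmetry.** AR(1) averaging 0.89 over three visits needs (2ρ + ρ²)/3 = 0.89, so ρ = 0.916 and ρ² = 0.839. For Month 12, k = (1 − 0.839)/(1 − 0.89) = 1.47, giving 6.4%. With three equally spaced visits the slope is the same contrast. The 2-df test is 3.3% by simulation. Milder decay (.91, .85) gives 3.0% and 5.5%.

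**First-choice Toeplitz** (REML with Satterthwaite df, N = 90, 4,000 runs per scenario):

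- GFS: Role, equal variances, constant or AR(1) correlation: 2.0-2.7% for all tests.
- SDs rising up to twofold over visits: 4-df test 3.1%, contrasts 2.4-3.0%.
- Baseline SD smaller than all later SDs: 4-df test 2.6-2.7%, contrasts 1.5-2.1%.
- MCCB: 2.3-3.0%.
- Large-sample check for GFS: Role with other assumed baseline SDs: Month 12 contrast 3.5-4.7% when baseline SD is 1.25-1.5 times the later SDs, and 0.7-1.5% when it is 0.6 times. The omnibus test stays at about 2.5-3.9%.

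Toeplitz converged in all 36,000 complete-data fits and all 830 fits with 20% dropout.

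**Unstructured alternative.** Parameters are m(m+1)/2: 6 for 3 visits, 15 for 5. On complete data the exact Hotelling test holds 2.5% under any covariance. A plain Wald F with N − 2 df gives 2.9% (N = 90, 5 visits), 3.1% (N = 72, 5 visits) and 2.6% (N = 90, 3 visits), so a small-sample correction is needed.

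**The case against.** Four points count against making more of this.

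1. The fallback runs only on non-convergence. Toeplitz has 3 or 5 covariance parameters here and never failed in the simulations. This stands, with the limit that those data were normal with random dropout. Real data could behave worse, but use of the fallback is probably uncommon.
2. Every inflated figure needs an assumed decay. This also stands: with the only correlations the documents give, taken as constant, the level is held. A reader might infer that the fallback simply doubles the GFS: Role error. The documents do not support that as a fact. With the average kept at 0.5, the 4-df test runs from 1.1 to 1.7 times nominal (2.7/2.5 to 4.2/2.5).
3. A reader might infer that false claims become two to four times as likely. That fits some Month 12 and slope results, not the omnibus test, which for MCCB is about 1.3 times nominal (3.3/2.5). Because the coding of time is unstated, the slope reading cannot be excluded, but neither is it the plan's declared test.
4. A reader might infer that Toeplitz itself gives wrong standard errors. It does not in general: it frees the correlation at each lag, which is what compound symmetry lacks. Section 7.1 concerns the pace of testing and also says stabilisation is meant to bring some clinical stability. It says nothing about variance.

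The primary Cox analysis is untouched. What remains is that a pre-specified fallback should be valid when it is used, and this one is valid only under a restriction that the plan does not justify.

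**Conclusion.** The point holds in conditional form. If Toeplitz fails to converge and correlation falls with lag, the GFS: Role error at a nominal 2.5% is about 2.7-5.5% (4-df test), 4-10% (Month 12 minus baseline) or 5-15% (slope). For MCCB it is about 3.3% (2-df) and about 6% (Month 12 or slope). The lower ends of the GFS: Role ranges come from mild decay around the plan's 0.5, and the upper ends from AR(1) with ρ up to 0.9, whose average correlation is above 0.5. Under constant correlation there is no inflation.

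The equal-variance restriction in Toeplitz is secondary: the omnibus test stays near nominal, and a Month 12 contrast can move in either direction under assumed SD ratios. This is a worthwhile, inexpensive improvement to the secondary analyses, not a defect that invalidates them.

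**What to change.** Amend Section 12.4 and the Synopsis to specify:

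- an unstructured covariance with Kenward-Roger degrees of freedom for both endpoints;
- on non-convergence, heterogeneous Toeplitz, then Toeplitz;
- compound symmetry only as a last resort, with small-sample-corrected sandwich standard errors.

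State also whether time is categorical or linear, since the size of the effect depends on it.

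The cost is SAP wording and a few more covariance parameters (6 instead of 3 for MCCB, 15 instead of 5 for GFS: Role), which is small with 90 patients. The Kenward-Roger model with dropout was not itself simulated here. The support for unstructured covariance is the exact complete-data result, and the Wald figures show why the small-sample correction belongs in the wording.
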